9.4. Lost to Follow-Up

Any subject without a LATITUDE Clarity device transmission within 90 days prior to each required data collection point may indicate a potential lost to follow-up subject. The investigator or designee shall make efforts to contact the subject in order to re-establish successful LATITUDE Clarity device transmission. Subjects will be classified as lost to follow-up on the End of Study CRF after three documented failed attempts (by either telephone call or certified letter) to contact them are documented in the study file. *Note: the end of study date should be on or after last documented contact attempt.*

9.5. Subject Status and Classification

Enrolled subjects will be classified as follows:

Intent refers to a subject who has been enrolled in the study but then does not have local anesthetic administered in preparation for a LUX-Dx ICM implant procedure. The original ICF and enrollment documentation for intent subjects should be maintained in the study file. The Intent subjects must be withdrawn from the study and the End of Study CRF completed. If the Intent subject is withdrawn due to reason of eligibility violation, a protocol deviation is required. There are no follow-up requirements for intent subjects.

Attempt refers to a subject who has been enrolled in the study, has had local anesthetic administered in preparation for the implant procedure of a LUX-Dx ICM, but is not successfully implanted with the LUX-Dx ICM. Attempt subjects must be followed at least 30 days post implant attempt and all reportable adverse events associated with the LUX-Dx ICM or attempted implant procedure must be reported and followed to resolution, or closure of the event with ongoing or chronic status. The safety check attempts must be made between 30 days and 60 days after the attempted implant procedure. These subjects must be withdrawn from the study and the End of Study CRF completed after the resolution of all reportable adverse events and the completion of the safety check.

Implant refers to a subject who has been enrolled in the study and is successfully implanted with the LUX-Dx ICM. These subjects are followed in accordance with the protocol and included in all applicable analyses.

9.6. End-of-Study Definition

End of Study occurs when all subjects have been enrolled, implanted, and followed for 12 months. Upon completion of participation in the study, subjects will be followed according to the site's standard of care.

10. Study Methods

10.1. Data Collection

The study data collection and follow-up schedule are shown in Table 10-1. Study data collection time-points are initiated from the date of the LUX-Dx ICM implant for each subject. *Note: the 6-month and 12-month EMR reviews do not require in-office visits but instead require the study sites to review a subject's electronic medical record (EMR) and reach the subject by phone/virtual health visit or in-office visit that might be standard of care for applicable study data.* A preliminary list of data collection items is provided in Appendix 26.1.

Form/Template 92120219_Rev/Ver D LUX-Dx PERFORM Protocol, 92557593, Rev/Ver C Page 30 of 66

		Implant Procedure Data Collection Points/Follow-up V		
Procedure/Assessment	Enrollment	(day=0) (within 30 days after enrollment)	2-Month (±30 Days)	6-Month (±30 Days), 12-Month ((±30 Days), End of Study
Informed consent	X			
Inclusion/ exclusion criteria	X			
Assessment of pregnancy for women of childbearing potential	X			
Demographics / physical assessment	X			
Medical history	X			
Implant procedure data		X		
Holter study			X*	
ICM reprogramming		Col	ect for each occurrence †	
EMR review and phone/virtual health visit or in-office visit per standard of care				Х
Ongoing AE assessment ¹ and protocol deviation		Collect	t as it occurs	

Table 10-1: Data Collection Schedule (Pre-implant Subject)

X=Required; X*=Required for approximately 600 subjects; --=Not required; \dagger =Only the first 5 are required to be entered in the database

¹ Reportable adverse events are defined in Section 19.1.

10.2. Study Candidate Screening and Recruitment

After the study site receives IRB/EC approval for the LUX-Dx PERFORM Study protocol and ICF, as well as the ATE by BSC, the Investigators may screen patients for inclusion in the study. Study recruitment will rely upon the general pool of ICM -indicated patients.

10.3. Informed Consent

The investigator and the designated site staff are responsible for obtaining eligible subject's written informed consent before any study-required procedure and data collection take place.

10.4. Enrollment Visit

All subjects who sign the IRB/EC-approved ICF will be considered enrolled in the study. The study site will collect baseline data from the subject's medical record and subject interview as outlined in Table 10-2. The "Reason for Monitoring" at the time of the enrollment will be used to determine which indications subgroup the subject belongs to.

Print any applicable Technical Source Form (TSF) for this visit. Data and source documentation requirements are summarized below in Table 10-2.

Form/Template 92120219 Rev/Ver D Confidential LUX-Dx PERFORM Protocol, 92557593, Rev/Ver C Page 31 of 66

Data Collection	Retention of Original Source Documentation
Informed consent documentation	Study Site
Inclusion/exclusion criteria	Study Site
Assessment of pregnancy for women of childbearing potential	Study Site
 Baseline data including: Demographics Medical history Physical assessment of weight and height 	Study Site

Table 10-2: Enrollment Visit Source Documentation

10.5. ICM Implant Procedure (within 30 days of Enrollment Visit)

The ICM implant procedure must occur within 30 days following enrollment. The procedure must be completed by an implanter authorized to perform the LUX-Dx ICM implant, and shall be performed according to the recommended implant technique described in the LUX-Dx ICM User's Manual. The study site will collect data associated with the implant procedure.

To obtain optimal sensing performance, it is strongly recommended to achieve a minimum of 0.2 mV in R-wave amplitude during the implant procedure. If this minimum value is not met, the ICM should be repositioned attempting to achieve a more desirable value before concluding the implant. Document any repositioning attempts in the appropriate CRF. Investigators are asked to follow the most current LUX-Dx ICM User's Manual for requirements or recommendations provided for the implant procedure.

Enrollment in LATITUDE Clarity can be performed prior to, during, or immediately after the implant procedure; however, registration of the LUX-Dx ICM device in LATITUDE Clarity requires the serial number of the ICM device and thus needs be performed after the implant. Device registration in LATITUDE Clarity must be completed within 7 days of the implant procedure. A copy of the LATITUDE Clarity programming report printed within 7 days of implant that displays a completed device set up serves as evidence that device registration is completed as required.

Print any applicable TSF and LATITUDE Clarity programming report (generated within 7 days of device implant). Data and source documentation requirements are summarized below in Table 10-3.

Form/Template 92120219_Rev/Ver D Confidential LUX-Dx PERFORM Protocol, 92557593, Rev/Ver C Page 32 of 66

Data Collection	Retention of Original Source Documentation
Implant procedure information including but not limited to:	
 Device implant procedure time, R-wave amplitude, repositioning attempt, and suturing technique Implanting facility: in-hospital vs. in-office Reason for unsuccessful implant 	Study Site
 Product information: ICM device details (model/serial, etc.) Implant tools and accessories used 	Study Site
ICM programming information	Study Site
Reportable adverse events (as defined in Section 19.1) and protocol deviations, if applicable	Study Site

Table 10-3: ICM Implant Procedure Source Documentation

10.6. ICM Reprogramming (throughout the study)

ICM reprogramming is defined as the modification of any programmable settings after the ICM is considered finally programmed following a successful implant and the subject is discharged from the implanting facility. Reprogramming can be achieved by using the remote programming feature via LATITUDE Clarity or performed during in-office visit. Because there may be many reprogramming attempts made on one subject, for the purpose of this study only the first 5 reprogramming events are required to be entered in the database per subject.

Reprogramming that are performed via the LATITUDE server but with the reprogrammed values not yet confirmed on the subject's ICM device are shown as "pending delivery to device" or similar message on the initial LATITUDE Clarity programming report. It is required that the reprogrammed values be delivered to the subject's device and a programming report be printed documenting the final delivery of the reprogrammed values. If the reprogrammed values continue to stay as "pending delivery to device", the site staff is asked to review the subject's monitoring status on the LATITUDE Clarity website to obtain issues identified by the system. This information will help the site staff troubleshoot and finalize the reprogrammed values, including contacting the subject to resolve connection issues.

The reason for reprogramming, methods of reprogramming (remotely or in-person), and confirmation of reprogramming completion must be reported on the appropriate CRF.

Print any applicable TSF and a copy of LATITUDE Clarity programming report documenting programming information each time that a device reprogramming is performed and successfully completed. Data and source documentation requirements are summarized below in Table 10-4.

Form/Template 92120219 Rev/Ver D Confidential LUX-Dx PERFORM Protocol, 92557593, Rev/Ver C Page 33 of 66

Data Collection	Retention of Original Source Documentation
ICM programming information following a device reprogramming	Study Site
Reportable adverse events (as defined in Section 19.1) and protocol deviations, if applicable	Study Site

Table 10-4: ICM Reprogramming Source Documentation

10.7. 2-Month Holter Study Visit (±30 days)

Approximately 600 subjects are required to complete the Holter study. While in-office visit is preferred for subjects to receive instructions from the study staff for wearing the Holter monitor, subjects may choose to complete this visit via a telephone call or virtual health visit as an alternative. This study procedure is performed at 2 months (±30 days) post-ICM implant.

At this visit, the appropriately trained/delegated study staff will apply the first Holter monitor and instruct the subject on the use of the device during the 14-day monitoring period. In case of by phone/virtual health visit, subject will receive the Holter monitor in the mail and selfapply the Holter monitor per instructions. After the first week the subject is required to remove the first Holter and apply a second Holter. It is highly recommended that the study staff call the subject during the monitoring period to ensure that the subject is applying the Holter monitor properly per instruction and help troubleshoot if there is any issue with the Holter monitor. At the end of the 14-day monitoring period, the subject will send both Holter monitors to the site using a pre-addressed shipping label. The Holter monitor data will be downloaded and transmitted or sent to the independent Core lab by the study staff for data collection. The site staff will clean and sanitize the Holter monitors for future use per site's standard of care methods and applicable labeled instructions provided by the product manual.

To obtain a sufficient number of extended Holter datasets from the "AF management, Post-AF ablation, or Suspected AF" subgroup (approximately 300), BSC will monitor the number of subjects enrolled in the Holter study and may close enrollment to other subgroups in order to achieve the required number of subjects from the "AF management, Post-AF ablation, or Suspected AF" sub-group. This is to ensure an appropriate distribution of the ICM indications. BSC may determine to end the Holter study early before enrollment of 600 subjects are reached, or extend the Holter study to more than 600 subjects mid-study due to inadequate amount of arrhythmia ECG data collected. Study sites will be notified by BSC when the Holter study has completed enrollment.

Print any applicable TSF for this visit. Data and source documentation requirements are summarized below in Table 10-5.

Form/Template 92120219_Rev/Ver D Confidential LUX-Dx PERFORM Protocol, 92557593, Rev/Ver C Page 34 of 66

Data Collection	Retention of Original Source Documentation
Information regarding the extended Holter monitor distribution, return, and data download and transmission	Study Site
Downloaded Holter monitor device raw data	Core lab and BSC
Extended Holter monitoring report and ECG strips	Core lab; a report copy is sent to BSC and Study Site
Reportable adverse events (as defined in Section 19.1) and protocol deviations, if applicable	Study Site

Table 10-5: 2-Month Holter Visit Source Documentation

10.8. 6-Month and 12-Month EMR Review (±30 days)

A review of each implanted subject's EMR must be performed at 6 months (\pm 30 days) and 12 months (\pm 30 days) post-ICM implant. Subjects are not required to visit the study site in-person. Reportable adverse events defined in Section 19.1 shall be collected. To supplement the EMR review, a phone call or virtual health visit to the subject must be attempted and documented to obtain adverse event information that may not be recorded in the EMR. If the subject is seen in-office that might be part of the standard-of care, then a phone call/virtual health visit is not required. It is not a study deviation if the subject cannot be reached by phone or virtual health visit despite attempts. In addition, any ICM reprogramming (to be documented throughout the study duration), arrhythmia diagnoses facilitated by the ICM, and the resulting arrhythmia treatments will be collected on the appropriate CRF. Site staff will confirm successful LATITUDE Clarity device transmission within the last 90 days to determine if the subject may be considered lost to follow-up.

Site is encouraged to perform the EMR review at the time of an in-office standard of care visit, if possible.

Print a copy of initial LATITUDE Clarity programming report to verify the time of the latest device transmission and print the applicable TSF for this visit. Data and source documentation requirements are summarized below in Table 10-6.

Data Collection	Retention of Original Source Documentation
ICM device transmission information	Study site
Information on arrhythmia diagnoses and related treatments since the LUXDx ICM implant	Study site
Reportable adverse events (as defined in Section 19.1) and protocol deviations, if applicable	Study Site

Table 10_6. 6.	and 12-Month	FMR Review	Source Documentation
1 abic 10-0. 0.	· and 12-month	THIN VENICA	Source Documentation

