5.3. LATITUDE Clarity Data Management System

LATITUDE Clarity Data Management System consists of a central LATITUDE server and website. LATITUDE Clarity is the website's diagnostics environment that is used to program the LUX-Dx ICM and to review and evaluate clinical data. All remotely transmitted data is sent to the LATITUDE server and is available on the LATITUDE Clarity website to authorized health care providers. Data stored on LATITUDE Clarity during subject's study participation will be used to support analysis of the study objectives.

System Component	Description	Model Number
ICM Device	LUX-Dx Insertable Cardiac Monitor (ICM)	M301
	myLUX software (patient app)	2925
Mobile Applications*	LUX-Dx Clinic Assistant software (clinic app)	2935
Server and Website	LATITUDE Clarity Data Management System	7260
Items Included in Package Additional Tools	The following sterile items are included in the package: • Insertable Cardiac Monitor device preloaded in the insertion tool • Incision tool • Sterile pouch	(part of M301)
Additional Tools used during implant, but not packaged with it	 Mobile device** with patient app or clinic app pre-installed Magnet Mobile device power adapter with USB cable (as needed) 	6259 myLUX 6256 LUX-Dx Clinic Assistant 6386 magnet

Table 5-1: BSC LUX-Dx ICM Device and Associated Components

*Future mobile or firmware applications may be used when they receive product clearance from regulatory agenc(ies)

**Including future mobile devices when they are available for use in the study

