11.1. Objectives

11.1.1. Primary Effectiveness Objective 1

The primary effectiveness objective 1 is to characterize the utilization of the remote programming feature.

11.1.1.1.Hypotheses

There is no formal hypothesis as this objective is exploratory.

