11.1.1.2. Sample Size

There is no formal hypothesis for primary effectiveness objective 1 and no formal sample size requirements for this objective. The overall sample size is driven by the primary effectiveness objective 2 and primary safety endpoint – acute. See section 11.1.5 for more details.

11.1.2. Primary Effectiveness Objective 2

The primary effectiveness objective 2 is to characterize the performance of arrhythmia detection algorithm.

11.1.2.1.Hypotheses

There is no formal hypothesis as this objective is exploratory.

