13.1. Data Collection, Processing, and Review

Subject data collected on the Case Report Form (CRF) will be recorded in a limited access secure electronic data capture (EDC) system.

The clinical database will reside on a production server hosted by Medidata EDC System. All changes made to the clinical data will be captured in an electronic audit trail and available for review by the sponsor or its representative. The associated Rave software and database have been designed to meet regulatory compliance for deployment as part of a validated system compliant with laws and regulations applicable to the conduct of clinical studies pertaining to the use of electronic records and signatures. Database backups are performed regularly.

The Investigator provides his/her electronic signature on the CRF in compliance with local regulations. Changes to data previously submitted to the sponsor require a new electronic signature by the Investigator acknowledging and approving the changes.

Visual and/or electronic data review will be performed to identify possible data discrepancies. Manual and/or automatic queries will be created in the Medidata EDC system and will be issued to the site for appropriate response. Site staff will be responsible for resolving all queries in the database.

All access to the clinical database will be changed to "Read only" after all data is either "Hard Locked" or "Entry Locked". Once acceptance of the final report or finalization of publications (as applicable) is received, final database storage and archiving activities can begin. Once all of the closeout activities are completed a request to IT is submitted to have the "Database Locked" or Decommissioned and all database access revoked.

In addition, electronic device data from the ICM system will be recorded using the LATITUDE Clarity data management system. This system was designed to be in compliance with federal regulations pertaining to electronic data. The LATITUDE Clarity Data Management System is secured with access limited to appropriately trained personnel and its data resides on Boston Scientific servers which perform regular backups.

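### Does requiring database entry of only the first 5 reprogramming events per subject spoil Primary Effectiveness Objective 1?

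*Combined protocol and SAP*

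**What the plan says.** Section 10.6 defines reprogramming as a change to any setting after final programming and discharge, done remotely through LATITUDE Clarity or at an office visit. It expects that some subjects may have many such changes and therefore says that "for the purpose of this study only the first 5 reprogramming events are required to be entered in the database per subject". The footnote to Table 10-1 (Section 10.1) repeats this: "Only the first 5 are required to be entered in the database". The table row carrying that footnote asks for collection at each occurrence.

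Section 10.6 also sets the content of the form: "The reason for reprogramming, methods of reprogramming (remotely or in-person), and confirmation of reprogramming completion must be reported on the appropriate CRF". It asks for a printed LATITUDE Clarity programming report each time a reprogramming is completed.

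Section 10.8 (6- and 12-month record review) lists among the items for the form "any ICM reprogramming (to be documented throughout the study duration", and does not repeat the limit of 5.

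On use of the data, Section 11.1.1 states: "The primary effectiveness objective 1 is to characterize the utilization of the remote programming feature". Section 11.1.1.2 adds: "There is no formal hypothesis for primary effectiveness objective 1 and no formal sample size requirements for this objective". Section 5.3 says: "Data stored on LATITUDE Clarity during subject's study participation will be used to support analysis of the study objectives", and Section 13.1 confirms that "electronic device data from the ICM system will be recorded using the LATITUDE Clarity data management system".

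**The concern.** Use of remote programming is the first primary objective and is named in the study title. If the analysis used only the entries that sites must make, four things would go wrong for subjects with more than 5 reprogrammings:

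- Their count would be censored at 5.
- A recorded 5 could mean exactly 5 or any larger number.
- Because 5 is a minimum, one site might stop there and another go on, so differences between sites could reflect entry habits.
- The remote share of reprogrammings would leave out later events, and would be biased if the mix of remote and in-office changes with event order.

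Section 10.8 adds doubt, because read alone it asks for all reprogrammings on the form. The method of reprogramming (remote or in-office) appears as a data item in Section 10.6 and Appendix A, both describing the form. At stake would be a descriptive result for a primary objective that partly measures the entry rule.

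**Working it through.** **1. Is there a figure to reproduce?** No. Objective 1 has no hypothesis, sample size or assumed event rate. Any size must rest on assumed rates.

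**2. How large could the loss be under a strict cap?** Let X be the reprogrammings per subject over about 12 months, with assumed means m of 1, 2, 3 and 5. Assume Poisson counts, or negative binomial (NB) counts with size k of 2, 1 or 0.5 for increasing concentration in a few subjects.

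- Events lost: L = 1 − E[min(X,5)] / m, where E[min(X,5)] is the sum of P(X ≥ j) for j = 1 to 5.
- Subjects affected: P(X > 5).
- Ambiguity of a recorded 5: P(X > 5) / P(X ≥ 5).

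Poisson, m = 3: E[min(X,5)] = 2.865, so L = 1 − 2.865/3 = 4.5%; P(X > 5) = 8.4%; ambiguity 45%.

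NB, k = 1, m = 3: P(X ≥ j) = 0.75^j, so E[min(X,5)] = 3 × (1 − 0.75^5) = 2.288, and L = 0.75^5 = 23.7%; P(X > 5) = 0.75^6 = 17.8%; ambiguity 0.75^6 / 0.75^5 = 75%.

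| Assumed mean | Lost, Poisson | Lost, NB k=2 | Lost, NB k=1 | Lost, NB k=0.5 | P(X>5), Poisson | P(X>5), NB k=1 |
|---|---|---|---|---|---|---|
| 1 | 0.1% | 1.1% | 3.1% | 8.3% | 0.1% | 1.6% |
| 2 | 1.1% | 7.0% | 13.2% | 23.3% | 1.7% | 8.8% |
| 3 | 4.5% | 15.6% | 23.7% | 35.2% | 8.4% | 17.8% |
| 5 | 17.5% | 31.9% | 40.2% | 50.7% | 38.4% | 33.5% |

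The error in the remote share is L × (remote share in events 6 and later − remote share in events 1 to 5). It is zero if the mix is stable. With an assumed 20-point shift after event 5, it is 20 × 0.045 = 0.9 points (Poisson, m = 3) or 20 × 0.237 = 4.7 points (NB k = 1, m = 3).

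The loss is negligible if reprogramming is rare and material if it is frequent or concentrated in a few subjects. The plan does not say which applies.

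**3. Does the plan put the analysis on capped data?** The places side by side:

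| Place | What it governs |
|---|---|
| Table 10-1 row | Collection at every occurrence |
| Table 10-1 footnote; 10.6 | Required database entry: first 5 |
| 10.6, closing instruction | Programming report for each completed reprogramming |
| 10.8 | Reprogramming documented throughout, collected at reviews |
| 5.3, 13.1 | Device data held in LATITUDE Clarity, to support the objectives |
| 11.1.1.3 | Objective 1 methods; listed in the contents, text not in the public copy |

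The Table 10-1 row and its footnote together give a workable reading: everything is collected and documented, and five entries are compulsory. Section 10.8 fits that reading; it simply lacks a cross-reference. Remote changes are made through LATITUDE Clarity, so they originate in a system without the entry limit.

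**4. What is untouched in any case?** The proportion of subjects ever reprogrammed, every subject with 5 or fewer events, and the first 5 events of everyone else.

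**The case for a change.** The strongest case for acting is that a descriptive objective is only as good as its description. No visible sentence says that Objective 1 counts come from LATITUDE Clarity, or that the server labels every event as remote or in-office. The sponsor itself foresees many reprogrammings in some subjects, and these heavy users are the ones truncated. Center poolability (Section 11.3.3) and subgroup analyses (Section 11.3.2) could pick up uneven entry as if it were a real difference. Naming the source and adding two totals to the existing 6- and 12-month forms would seem cheap.

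Part of this stands. Whether the server records the method for in-office events cannot be confirmed from the text, and a CRF-only summary without a label would mislead. But the source may well be named in Section 11.1.1.3, whose absence from the public copy is not a gap in the plan. The preferred remedy, taking counts from LATITUDE Clarity, largely restates Section 5.3. The visible plan does not name mean events per subject or remote share as outcomes. Changing Section 10.6, 10.8 or Table 10-1 is also not free: under Section 16.3 every protocol amendment needs IRB/EC approval before it takes effect, here at up to 35 sites, and new form fields add site and database work.

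**Conclusion.** No change to the plan is needed. The cap is real, but it limits required entry and not what is collected or documented. The revision history lists it as an intended modification, and Section 10.6 gives the reason for it. Keeping detailed entry to five events is a fair exchange for less site work in an observational study whose Objective 1 is exploratory.

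The harm depends on a condition the documents do not establish: that totals are taken only from capped entries. If they were, the loss could be anywhere from 0.1% to 50.7% of events under the assumed means of 1 to 5 and the Poisson or NB counts above. That spread comes from the assumptions, since the plan gives no rate. No test, alpha, power or sample size is affected under any of them.

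What is left is ordinary analyst practice: take total counts from LATITUDE Clarity where available, and describe any summary built on form entries alone as covering the first 5 events, or show the top category as 5 or more. A pointer from Section 10.8 to the limit in Section 10.6 would be tidy if the protocol is amended for another reason. The conclusion would need another look only if Section 11.1.1.3 commits Objective 1 totals to the form entries alone.
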